#### **Box 1. Data sources to derive the Long COVID cohort and assess patient reported outcomes**

### **Clinical Practice Research Datalink (CPRD)**

Clinical Practice Research Datalink (CPRD) is a real-world research service supporting retrospective and prospective public health and clinical studies. CPRD is jointly sponsored by the Medicines and Healthcare products Regulatory Agency and the National Institute for Health Research (NIHR), as part of the Department of Health and Social Care. CPRD collects anonymised patient data from a network of GP practices across the UK. Primary care data are linked to a range of other health related data to provide a longitudinal, representative UK population health dataset. The data encompass 60 million patients, including 16 million currently registered patients.

CPRD primary care data is linked to Hospital Episode Statistics, (HES) COVID-19 Hospitalisation in England Surveillance System (CHESS) and Second-Generation Surveillance (SGSS) data via a unique patient pseudo-identifier which allows this data to be linked together to create a combined dataset for analysis.

### **Second-Generation Surveillance System (SGSS)**

SGSS is the national laboratory reporting system used in England to capture routine laboratory data on infectious diseases and antimicrobial resistance. The SARS-CoV-2 testing started in UK laboratories on 24/02/2020, with the SGSS data reflecting testing (swab samples, PCR test method) offered to those in hospital and NHS key workers (i.e., Pillar 1). The linked SGSS data only contains positive tests results. The primary care data itself includes both positive and negative Pillar 2 PCR and other RNA detection COVID-19 test results and it is estimated that over 80% of all such tests undertaken in England are being matched to GP records.

### **Hospital Episode Statistics (HES)**

HES Admitted Patient Care (HES APC) data contains details of all admissions to, or attendances at English NHS healthcare providers. It includes private patients treated in NHS hospitals, patients who are resident outside of England and care delivered by treatment centres (including those in the independent sector) funded by the NHS. All NHS healthcare providers in England, including acute hospital trusts, primary care trusts and mental health trusts provide data. HES APC data includes the complete set of hospital episode information (admission and discharge dates, diagnoses (identifying primary diagnosis), specialists seen under and procedures undertaken) for each linked patient with a hospitalisation record. In addition, Augmented care data (intensive and/or high dependency levels of care) and Maternity data are available.

### **COVID-19 Hospitalisation in England Surveillance System (CHESS)**

CHESS was established by Public Health England (PHE) across all NHS Trusts in England on 15/03/2020 to collect epidemiological data on COVID-19 infection in persons requiring hospitalisation and ICU/HDU admission. It has more details over HES including laboratory test results for COVID-19 and other respiratory viruses, mechanical ventilation, complications like pneumonia, COVID-19 specific risk factors and treatment.

## **Development and validation of a new patient reported outcome (PRO) measure of symptom burden in individuals with Long COVID (Objective 2)**

We will follow international best practice guidance in the development of PRO measures to construct and evaluate the psychometric measurement properties of a new PRO measure that will assess symptom severity and interference in the population of individuals with Long COVID, the Symptom Burden Questionnaire™ for Long Covid (SBQ-LC™).

Ethical approval for SBQ-LC™ development has been granted by the University of Birmingham based on a separate linked protocol with participants recruited via non-NHS routes (Reference ERN\_21-0191). Evaluation of the SBQ-LC™'s psychometric measurement properties will be undertaken utilising study data collected via the Aparito Atom5™ digital platform collected in WP1.

**Collection of validated patient-reported outcomes (PROs) including symptoms, quality of life and work capability data longitudinally from the representative cohort of individuals with Long COVID using Aparito Atom5™ (Objective 3)**

Aparito Atom5™ is a digital platform with a patient facing mobile application (iOS and Android) and online portal. It has a number of capabilities that make it ideally suited to study Long COVID. These include the capability to: track quality of life and work capability with the use of electronic PROs, integrate wearable devices, allow direct communication via healthcare professionals, deliver tailored notifications and alerts with links to relevant support services, and convey data in real-time to clinicians and researchers.

The Aparito Atom5™ app is available for use on Android and iOS operating. Atom5™ is a highly configurable, disease agnostic and multilingual platform designed to support research and clinical trials. It has five components: patient facing desktop portal, patient facing app (iOS and Android), clinician/study staff-facing desktop portal, hardware/wearable integration, and data analytics dashboard. Each deployment is GxP compliant. Aparito is accredited for Quality Management System (QMS), ISO 13485 and Information Security Management System (ISMS) ISO 27001. The online portal can be accessed through an internet browser.

Participants will be e-consented to use the Atom5™ platform and asked about the presence of comorbidities, established Long COVID symptoms, quality of life and work/education capability using validated tools via a study specific smartphone app. They will also be asked if they have previously been hospitalised for COVID-19 and if they have received a vaccine for SARS CoV-2.

**Outputs and deliverables:** A population-based representative cohort of individuals with Long COVID and two groups of propensity score matched control participants [(i) without COVID-19, (ii) with COVID-19 but without Long COVID]. This will include detailed data on symptoms, quality of life, work capability and objective health measures for individuals with Long COVID and matched controls. We will also have validated of a new disease-specific PRO of symptom severity and interference for individuals with Long COVID.

**WP2: Analysis and confirmation of distinct Long COVID syndromes (Objectives 4 and 5)**

**Overview:** Long COVID may be a heterogeneous group of post-viral syndromes affecting multiple body systems and pathophysiological pathways. It is important to describe the heterogeneity of symptoms and identify whether there are distinct clinical phenotypes. This will enable identification of individuals with distinct syndromes for further detailed study, including understanding differences in immunological response, and to develop targeted approaches.

**Data-driven analysis to identify distinct Long COVID syndromes (Objective 4, part A)**

We will define distinct symptom clusters (syndromes) using linked data from CPRD and Atom5™ platforms. We will employ clustering algorithms that have been shown to work well in medical settings, with binary and mixed variables: (1) complete linkage hierarchical clustering; (2) probabilistic c-means cluster analysis; (3) density peaked clustering analysis. We will evaluate algorithm performance and the optimal number of clusters (e.g. by internal validation against a holdout dataset using metrics such as Gap statistic and silhouette index).

We will describe the epidemiology of patients within each Long COVID syndrome as well as health service use (primary care consultations, prescriptions, A&E attendances and hospital admissions) and mortality risk and compare these to both sets of matched control patients. We will identify whether Long COVID syndromes are

associated with particular population groups such as BAME groups, patients with long-term conditions, and other vulnerable population groups identified by Public Health England.

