### 1.0 Background

Coronavirus Disease 2019 (COVID-19), caused by Severe Acute Respiratory Syndrome Coronavirus 2 (SARS CoV-2), is the most significant pandemic since the Spanish Influenza Pandemic of 1918. There have been over 140 million cases worldwide, including over 4.4 million cases in the UK. In the UK, this has resulted in over 460,000 hospital admissions and in excess of 150,000 deaths.

SARS CoV-2 enters human cells using the angiotensin II receptor, which is widely expressed throughout the body. COVID-19 is consequently a multisystem disorder affecting the lungs, heart, gut, kidneys, brain and skin. A wide range of symptoms have been associated with COVID-19 including breathlessness, fatigue, fever, myalgia, “brain fog” and anosmia.

These symptoms resolve within 12 weeks in most affected individuals. However, in up to 10% of individuals, symptoms of COVID-19 persist, sometimes in a relapsing remitting manner. This can have significant impacts on physical and neurocognitive functioning, quality of life and work capability. Those having symptoms lasting beyond 12 weeks are referred to as experiencing post-COVID-19 syndrome (NICE 2019) or more widely known as Long COVID.

The cause of Long COVID is poorly understood. However, there is evidence from other post-viral syndromes that may be applicable to Long COVID. Furthermore, evidence from existing studies on COVID-19 suggest a significant burden of pathophysiological insults and sequelae such as lung scarring, kidney injury, myocarditis and systemic inflammatory states that may promulgate longer term symptoms. There is also a possibility that autoimmune pathways may be triggered by COVID-19, leading to multi-system inflammatory damage.

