## 6.0. Participant selection and Eligibility

### 6.1 Population-based representative cohort of individuals with COVID-19 (minimum 2000 participants)

#### 6.1.1 Eligibility Criteria

Non-hospitalised individuals with a positive RT-PCR test for SARS-CoV-2 in SGSS data linked to CPRD Aurum. Those from that cohort reporting symptoms associated with COVID-19 at least 12 weeks from the diagnosis will be defined as having Long COVID.

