#### 6.1.2 Inclusion criteria

Non-hospitalised individuals aged 18 years and over with a SARS CoV-2 RT-PCR result in SGSS data linked to CPRD Aurum, and willing to provide informed consent and to undertake the protocol activities.

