#### 6.1.3 Exclusion criteria

Individuals without a positive SARS CoV-2 RT-PCR test result in CPRD Aurum.

Individuals with a hospital admission within 28 days of a positive SARS CoV-2 RT-PCR result in CPRD AURUM.

Individuals aged under 18 years.

Individuals unable/unwilling to provide informed consent.

Individuals unable/unwilling to undertake the protocol activities.

Individuals deemed appropriate for exclusion by their GP (e.g., on a palliative care register).

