## **10.0 Data Analysis Plan**

### **10.1 Long COVID symptom clusters**

Unsupervised exploratory clustering techniques will be employed to identify distinct Long COVID symptom clusters (objective 4).

We will first perform dimension reduction using one of: multi-dimensional scaling (MDS), t-stochastic neighbour embedding (t-SNE) and uniform manifold approximation and projection (UMAP). This first step will reduce dimensionality of the global data set while retaining local distances between individuals.

Following the dimensionality reduction step, we will employ clustering algorithms that have been shown to work well in medical settings:

- (1) k-means clustering, which locates the stable set of centroids of a predetermined number of k clusters.
- (2) Fuzzy c-means cluster analysis, a version of k-means clustering which allows data points to have partial cluster membership.

(3) Hierarchical agglomerative clustering, which joins observations in a recursive fashion satisfying some linkage criterion until  $k$  clusters have been generated. We will use the Ward linkage, which joins observations that minimise the variance of merged clusters.

(4) Gaussian finite mixture models, a model-based approach to clustering which associate each data point with a multivariate (ellipsoidal) Gaussian distribution.

(5) DBSCAN/HDBSCAN, algorithms, which identify clusters of dense observations among unassigned lower-density observations.

The optimal number of clusters for all methods (except DBSCAN) will be determined using model selection methods and internal cross validation. Cluster membership goodness of fit will be evaluated by: (1) the Jaccard similarities (intersection size divided by union size) of the original clusters to the most similar clusters in the resampled data, and (2) the average silhouette score, where the silhouette score varies between +1 for an observation aligned with its cluster centre and -1 for an observation aligned with the centre of another cluster. We will determine mean bootstrapped Jaccard and silhouette indices to assess cluster stability. The plot of within-groups sum of squares vs  $K$  will be checked graphically for optimal  $K$  (elbow method) and a minimum BIC.

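### Symptom clusters will be read as distinct syndromes, but time since infection is open-ended above 12 weeks and no named check compares clusters on it

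*Protocol*

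**What the plan says.** Clusters and syndromes are treated as the same thing. Section 5.0 (WP2, Objective 4, part A) states: "We will define distinct symptom clusters (syndromes) using linked data from CPRD and Atom5™ platforms".

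The clustered group is defined by a minimum duration only. Section 6.1.1 reads: "Those from that cohort reporting symptoms associated with COVID-19 at least 12 weeks from the diagnosis will be defined as having Long COVID". The inclusion criterion in 6.1.2 takes "Non-hospitalised individuals aged 18 years and over with a SARS CoV-2 RT-PCR result in SGSS data linked to CPRD Aurum", with no earliest or latest test date. The only time-related exclusion of cases in 6.1.3 concerns "Individuals with a hospital admission within 28 days of a positive SARS CoV-2 RT-PCR result in CPRD AURUM". Box 1 dates the start of testing: "The SARS-CoV-2 testing started in UK laboratories on 24/02/2020". Section 8.1 and Table 1.0 time the monthly reports from enrolment, not from infection.

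Section 5.0 plans validation on a holdout dataset with measures such as the Gap statistic and silhouette. Section 10.1 adds an elbow plot and BIC, and says: "We will determine mean bootstrapped Jaccard and silhouette indices to assess cluster stability". The planned description of clusters in 5.0 lists population groups, long-term conditions, health service use and mortality. It does not list illness duration.

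The Background (1.0) accepts that symptoms change over time, persisting "sometimes in a relapsing remitting manner".

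**The concern.** If the symptom mix shifts as the illness ages, people with one and the same illness can separate into an early and a late group simply because they report at different times after infection. A bootstrap or random holdout reproduces the same mix of durations, so such a split can recur without being a syndrome.

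The labels are used before anyone would revisit them. Section 6.5.3 samples 50 people from each of the four most prevalent syndromes, and 11.1 sends invitations 3 months after enrolment. The between-syndrome immune and protein comparisons (5.0, 11.4, 14.2) and the mapping of therapies to syndromes (WP3) rest on the same labels. If a cluster is a stage, a biomarker difference may reflect time since infection, and a therapy may be mapped to a phase that participants pass through. Later analysis can adjust for this, but it cannot change who was sampled.

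**Working it through.** **1. Range of time since infection.** Inputs: testing start 24/02/2020 (Box 1), version date 05/07/2021 (version control log), minimum 12 weeks (6.1.1).
- 24/02/2020 to 05/07/2021 = 497 days; 497/7 = 71 weeks; 497/30.44 = 16.3 months.
- Permitted span at the version date: 12 to 71 weeks, a ratio of 71/12 = 5.9.

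This is what the criteria allow. The protocol gives no observed distribution.

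**2. The plan's own figures.**
- Section 14.1: 5% x 500 = 25 people in the smallest cluster, inside the stated 20 to 30.
- Table 3 (Kruskal-Wallis, 50 v 50, alpha 0.05) reproduces within 2 points in every row over 20,000 simulated trials per row. At d = 0.6 the result was 82.6% against the stated 80.8% (normal), and 72.2% against 71.7% (t5).

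Both take the clusters as given, so neither bears on stage versus syndrome.

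**3. What the named checks use.** Silhouette for person i is (b - a)/max(a, b), with a the mean distance to the person's own cluster and b that to the nearest other cluster. Jaccard is the size of the intersection divided by the size of the union of original and resampled cluster. Gap, elbow and BIC are likewise functions of the clustered data and the partition. Time since infection is not named as an input. If two mechanisms give the same symptom distribution, these indices have the same expected value under both.

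**4. Illustration with a fairly sharp change (assumed).** n = 500; 20 binary symptoms; weeks t within 12 to 71, uniform or in two waves. Let s = 1/(1 + exp(-(t - 41)/4)). Ten symptoms have probability hi - (hi - lo)s and ten have lo + (hi - lo)s. In the comparator, s is shuffled so that it is unrelated to time. Two-dimensional MDS was followed by k-means with K = 2. Six scenarios were run (hi/lo of 0.5/0.3, 0.6/0.2 and 0.7/0.2, under each time pattern).

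| Measure | Stages of one illness | Unrelated to time |
|---|---|---|
| Silhouette | 0.34 to 0.61 | 0.34 to 0.60 |
| Bootstrapped Jaccard | 0.84 to 0.99 | 0.86 to 0.99 |
| R-squared, cluster with weeks since infection | 0.25 to 0.86 | 0.00 |

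For 0.6/0.2 with uniform times, median weeks since infection in the two clusters were 27 and 56 (stages) against 41 and 43 (unrelated). The symptom indices agree by construction. Only a comparison on time separates the two cases.

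**5. Illustration with gradual drift (assumed).** One syndrome; n = 500; uniform over 3 to 17 months; 15 binary symptoms, of which 5 fall, 5 rise and 5 stay constant. A log-odds slope of 0.15 per month over 7 months either side of the midpoint gives 1.05, so 74% falls to 26%. Ranges are over repeat runs; aligned means everyone at the same time since infection.

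| Slope 0.15 | Spread over 3 to 17 months | Aligned |
|---|---|---|
| Jaccard, K = 2, raw symptoms | 0.82 to 0.84 | 0.47 to 0.50 |
| Jaccard, K = 2, after MDS | 0.93 to 0.94 | 0.71 to 0.73 |
| Jaccard, K = 4, after MDS | 0.78 to 0.82 | 0.67 to 0.80 |

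The K = 2 clusters on raw symptoms differed by 4.7 months in mean time since infection. On raw symptoms the silhouette was about 0.08, and Jaccard at K = 4 was 0.39 to 0.40. With a weaker slope of 0.10, Jaccard at K = 2 was only 0.60.

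**The case against.** The strongest reply has four parts.

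*This is detail for the analysis plan.* Which monthly report is clustered and which variables describe the clusters may well be settled in an SAP that is not shown, and 10.1 calls the clustering exploratory. That stands for those details, and their absence is not the point. The protocol itself fixes the open-ended definition, equates clusters with syndromes and names the checks.

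*The checks would warn.* A reader might infer that the planned checks would certify stages as stable syndromes. The documents do not support that. They name several checks, and under gradual drift some of them signalled trouble: the low raw silhouette and K = 4 Jaccard above, and a Gaussian-mixture BIC that chose one cluster in 8 of 8 runs (slope 0.15) and 4 of 8 (slope 0.20). Others did not: Gap mostly chose two clusters, and silhouette after MDS was 0.36 to 0.41. A warning of this kind shows weak structure; it does not point to time as the cause.

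*The drift is assumed.* This stands. No section gives symptom prevalence by time, and a relapsing-remitting course is not a steady early-to-late shift. The early tail may also be thin, since Box 1 says SGSS reflected testing of hospital patients and NHS key workers, and admissions within 28 days are excluded.

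*Movement between clusters proves little.* A reader might take the simulated 40% to 41% who change cluster after six months (slope 0.15) as evidence of staging. Redrawing symptoms at the same time since infection already moves 33% to 34%, so most of it is noise and the figure carries no weight here.

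**Conclusion.** The point holds in a limited form. The criteria allow reports from about 3 to 16 months after infection at the version date, and nothing in the stated clustering plan compares clusters on that interval. The named checks are therefore not designed to separate a stage from a syndrome.

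It does not follow that the clusters will be stages, or that every planned check would pass them. Both depend on how symptoms change with time and on the actual spread of test dates, and the protocol gives neither. The simulations show a possible mechanism and do not estimate its frequency.

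This is a cheap improvement to make before participants are selected for bio-sampling. It is not a defect that invalidates the clustering.

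**What to change.** Add to sections 5.0 and 10.1:

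1. Before BioWear selection, report the distribution of time since the positive test (SGSS date) for each cluster. Describe a cluster that differs mainly by it as a possible stage, not a distinct syndrome.
2. Apply the fixed cluster rule to later monthly reports and state how many people stay. Judge this against the change expected from report-to-report variation alone, for which adjacent monthly reports could serve. Use reports up to month 3 before sampling and later ones for interpretation, because 11.1 places the invitations 3 months after enrolment.
3. Adjust the between-syndrome biomarker comparisons for time since test, or stratify by it. The Kruskal-Wallis test in 14.2 takes no covariate, so a stratified rank test or a regression model would be needed.

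Clustering separately in bands of time since test should be a sensitivity analysis only. Two bands of 500/2 = 250 leave a 5% cluster with 0.05 x 250 = 12.5, about 12 people, below the 20 to 30 in 14.1. Even at the hoped-for 750 it is 0.05 x 375 = 18.75. Aligning everyone on one time is not possible either: someone who enrols at 3 months reports over months 3 to 15, and someone who enrols at 16 months reports over months 16 to 28.

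Cost: wording and a little more analysis, using the SGSS linkage and monthly reports already planned. Some clusters may be reported less firmly as syndromes. Where clusters barely overlap in time since test, adjustment cannot separate the two explanations, and the report should say so.

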## 8.0 Study procedures

### 8.1 Population-based representative cohort of individuals with long COVID and matched controls

Eligible individuals who wish to participate will download the Aparito Atom5™ app or visit the website and register using their unique one-time use on-boarding code. They will then be asked to provide electronic consent on the app or website, which includes confirming that participants with a positive SARS CoV-2 RT-PCR result have not been hospitalised within 28 days of being diagnosed with COVID-19. Control participants will be asked if they have ever had COVID-19 to check eligibility for inclusion as a control subject. Once the consent form has been completed, participants will be asked to complete a brief demographic and clinical questionnaire. The questionnaire will ask for the following details: name, sex, date of birth, contact number, postal address, ethnic group, GP address, height, weight, smoking status, pregnancy status, SARS CoV-2 vaccination status, confinement (shielding) status, care home residence, occupation, occupational status (in work, furlough, etc.), and over-the-counter medications used to manage symptoms. Full details of these questions are provided in the appendix (Baseline data collection in Atom5™) and in Table 1.0.

Participants will then be invited to report the presence of established Long COVID symptoms and quality of life using validated tools at monthly intervals for a period of 12 months. At each time point, participants will be asked to confirm their willingness to continue to participate in the study. Those wishing to withdraw will be asked to complete a withdrawal form and advised that any data collected up to that point will need to be retained as it will have been used in aggregated data analyses.

As requested by our PPI group, we will ensure that people who are unable to use the app or website (due to no access to a smartphone or internet connection, patient preference, language, or other requirements) can participate through nurse interview-led appointments (telephone or video conference) with translators as required. Information and contact numbers will be provided on the PIS. Alternative language versions of each PRO will be provided where validated translations exist (see table below) The translated questionnaires are currently being programmed on the app.

	English	Bengali	Polish	Welsh	Punjabi	Gujarati	Urdu
EQ5D5L	X	X	X	X	X	X	X
FACIT F	X	X	X		X	X	X
PHQ-2	X	X	X		X	X	
GAD-2	X		X		X	X	X

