PCL-2	X						
modified MRC Dyspnoea Scale	X						
COVID-19 core outcome measure for recovery	X						
SBQ-LC	X						

All participants will be advised where to seek additional support should completion of the PROs raise any concerns regarding their well-being. Proxy-completion will be permitted via the app or website, or via telephone if the participant is unable to complete the PRO and will be documented on the app or website, or via the clinical portal.

Participants will be sent push notification reminders each month to complete the questionnaires on the day completion is due, at 2 days and again at 6 days. Both research personnel and patients will be provided with training resources and telephone support to help minimise missing data. Aparito will provide up to a maximum of two training sessions to the site staff online. A training video will be made available for those that need training after those two sessions. Finally, the site staff will be made aware of the IT support procedures and how to contact Aparito as needed. Aparito will be responsible for providing first line support only to the clinical team via UoB during the duration of the project. Training leaflets outlining how to download and use the app will be provided to staff and patients.

The health service use (primary care consultations, prescriptions, A&E attendances and hospital admissions) and mortality of patients from each Long COVID syndrome will also be described using data from CPRD Aurum and linked data from Hospital Episode Statistics and Office for National Statistics mortality statistics (via CPRD). We aim to use the most up-to-date healthcare data available from CPRD available up to 12 months of follow-up from initial registration on Atom5™.

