## **8.2 Clinical support**

The majority of symptoms of long COVID, while potentially debilitating, are not associated with acute medical emergencies. However, some symptoms of long COVID can be distressing, and also can mirror symptoms of potentially dangerous medical conditions, such as a blood clot or stroke. The TLC study cannot provide overarching medical care for participants, and their care remains with their usual care providers.

To provide support and guidance, access to nurse-led clinical support (during usual working hours of 8am - 5pm, Monday-Friday (excluding public holidays)) with oversight by a consultant respiratory physician ([name]) will be provided for participants reporting severe symptoms on Atom5™. [name] will be mentoring and supporting the nurses, providing medical guidance when needed by answering the nurses queries and ensuring signposting to appropriate medical services, as needed. This might include reviewing questionnaire answers from participants, speaking to participants should any severe symptoms be flagged or should the participant wish to speak to a doctor involved in the TLC study, or speaking to the participant's usual medical practitioner to discuss responses to the questionnaires. [name] can only provide signposting advice (including asking the participant to present to hospital for an emergency review if needed), to ensure appropriate safety netting for the participant, and cannot provide medical treatments or further investigation, as the participant will remain under the care of their usual medical practitioner.

Should participants be concerned about their symptoms or experience a sudden deterioration in their symptoms, they will be encouraged to discuss this with their GP, call 111 or 999, depending on the severity of their symptoms, as per usual standard of care practices and as advised by the medically qualified support team. This will be explained on the PIS. The nurse-led support team can signpost to medical assistance, but will not be able to provide direct medical care or aid.

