GPs or the participants' usual care team will not be routinely informed about the results of the research or the data collected. However, Atom5™ will be configured to report the recording of severe symptoms to the research nurse via the Atom5™ clinical portal. The research nurse will then contact the participant to assess the level of support needed and signpost to relevant services and information or escalated to the consultant physician for further advice if needed. The advice given may include a recommendation for the participant to contact their GP or NHS 111 to discuss their symptoms or seek more urgent help by contacting 999. The participant's GP will only be contacted if the participant cannot be reached after three attempts over the

course of 24 hours and the participant has provided their GP details. We will seek specific consent for these actions. Any verbal contact with the participant or GP will be followed by a written letter.

Participants will be advised in the PIS and in the Atom5™ app and website that the data will not routinely be seen by their GP or usual care team. If they are concerned about symptoms or well-being they should dial 111. In an emergency they should dial 999. They will also be provided with the link to the NHS Your COVID Recovery website (<https://www.yourcovidrecovery.nhs.uk>). Participants reporting symptoms of urgent clinical concern will receive the following notification on Atom5™: “You have reported symptoms that may require urgent follow-up. We recommend you contact 111 to seek further advice. In an emergency dial 999.”

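### Care contacts prompted by the severe-symptom route may bias the health service use comparison upward for Long COVID, and the protocol states no means of separating them

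*Protocol*

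**What the plan says.** **The outcome.** Protocol 5.0, WP2, Objective 4 part A, will describe for each Long COVID syndrome "health service use (primary care consultations, prescriptions, A&E attendances and hospital admissions) and mortality risk and compare these to both sets" of matched controls.

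**The period.** Section 8.1 draws these data from CPRD Aurum with linked hospital and mortality records, "available up to 12 months of follow-up from initial registration on Atom5™". The same section asks participants to report symptoms "at monthly intervals for a period of 12 months", and Table 1.0 adds a baseline questionnaire.

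**The safety route.** Section 8.2 says that nurse-led support "will be provided for participants reporting severe symptoms on Atom5™". The platform reports severe symptoms to the research nurse, who then contacts the participant. "The advice given may include a recommendation for the participant to contact their GP or NHS 111 to discuss their symptoms", or to seek more urgent help through 999. The supervising physician can give signposting advice, "including asking the participant to present to hospital for an emergency review if needed". Reports of urgent concern also produce an automatic message recommending 111, or 999 in an emergency. The study contacts the GP only if the participant cannot be reached after three attempts over 24 hours and has given GP details. Section 15.1 adds rapid referral to the Long COVID clinic if required.

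**The groups.** Under 6.3.1, Control Group 2 consists of participants with a positive test who do not report symptoms on Atom5 beyond 12 weeks. Control Group 1 has no COVID-19 diagnosis and completes the same questionnaires.

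**The concern.** GP consultations, A&E attendances and admissions appear twice in the protocol: as possible results of a study procedure, and as outcomes compared between groups over the same months. If that procedure acted equally on all groups it would create no difference where none exists. But it responds to symptom severity, which is closely tied to how the groups are formed. Some of the apparent excess use in Long COVID could therefore come from being in the study. The ordering of the syndromes could also shift, because syndromes are symptom clusters and may trigger alerts at different rates.

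This matters because section 2.0 wants a representative cohort in order to understand the burden of Long COVID. Contacts that happen because a study nurse called are not part of the burden in people outside the study.

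**Working it through.** The protocol states no rate, effect size or power for this comparison, so there is no figure of its own to reproduce. The check has two parts.

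**1. Which products of the route are counted as outcomes?**

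| Possible result of the route | Listed outcome in WP2? |
|---|---|
| GP consultation after nurse advice | Yes |
| Prescription issued at that consultation | Yes |
| A&E attendance or admission after advice to go to hospital or call 999 | Yes |
| 111 or 999 call in itself | No; counts only if it leads to a listed contact |
| Long COVID clinic attendance | No; counts only if it leads to a listed contact |

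For Control Group 2, unequal triggering is expected from the definition: the reports that would raise alerts are the reports that would take a participant out of the group. For Control Group 1 it is an expectation only, since that group is not selected on symptoms.

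**2. How large could the effect be?** Every input here is an assumption.

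- λ₀: listed contacts per control per year without the route (primary care 4 to 8; A&E 0.2 to 0.4)
- RR: true rate ratio, Long COVID to control
- f₁, f₀: share flagged as severe in Long COVID and in controls
- k: net extra contacts per flagged person (primary care 0.5 to 2; A&E 0.05 to 0.2)

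Observed RR = (λ₀·RR + f₁·k) / (λ₀ + f₀·k)

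Example for primary care, with λ₀ = 4, RR = 1, f₁ = 0.30, f₀ = 0.05, k = 1: (4 + 0.30) / (4 + 0.05) = 4.30 / 4.05 = 1.06.

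The lower end of each range below uses the highest λ₀ with the lowest k, and the upper end the reverse. For equal flagging at a true RR of 1.5 the two ends swap.

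| Outcome | Flagged, Long COVID v control | True RR | Observed RR |
|---|---|---|---|
| Primary care | 10% v 2% | 1.0 | 8.05/8.01 = 1.005 to 4.20/4.04 = 1.04 |
| Primary care | 30% v 5% | 1.0 | 8.15/8.025 = 1.02 to 4.60/4.10 = 1.12 |
| Primary care | 50% v 5% | 1.0 | 8.25/8.025 = 1.03 to 5.00/4.10 = 1.22 |
| Primary care | 30% v 5% | 1.5 | 12.15/8.025 = 1.51 to 6.60/4.10 = 1.61 |
| A&E | 10% v 2% | 1.0 | 0.405/0.401 = 1.01 to 0.220/0.204 = 1.08 |
| A&E | 30% v 5% | 1.0 | 0.415/0.4025 = 1.03 to 0.260/0.210 = 1.24 |
| Primary care or A&E | 30% v 30% | 1.0 | 1.00 |
| Primary care | 30% v 30% | 1.5 | 6.60/4.60 = 1.43 to 12.15/8.15 = 1.49 |

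Two things follow. Upward bias needs more flagging in Long COVID than in controls; equal flagging gives none at a true ratio of 1.0 and slight dilution at 1.5. And over these ranges the distortion runs from negligible to more than 20%, so its importance depends on quantities that the protocol does not give.

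**The case against.** Several points on the other side stand and limit what can be said.

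- **The route is not confined to Long COVID.** Section 8.2 offers it to any participant reporting severe symptoms, and section 8.1 advises all participants where to seek support. Only the frequency of triggering is expected to differ.
- **The advice is conditional.** GP and hospital advice is given only where the nurse or physician thinks it needed, and section 8.2 describes encouragement to use the GP, 111 or 999 as usual care. Some of these contacts would have happened anyway.
- **The direction is likely, not certain.** Nurse support and signposting to self-management could replace some GP visits, which would make k smaller or negative.
- **Prompted contacts are not beyond recovery.** A reader might take the silence of Table 1.0 on alerts to mean that they can never be identified. Table 1.0 is a schedule of participant data collection, not an inventory of platform records. Section 9.5.1 stores questionnaire responses on Atom5, and section 8.2 requires a letter after verbal contact. Alerts and calls could be partly rebuilt, but the advice given and its date are not stated to be kept as research data.
- **The comparison is descriptive.** It has no primary status and no power claim.

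It can also be said that a sensitivity analysis belongs in the statistical analysis plan, which is not shown. That is fair for the analysis itself. It does not cover the recording: an analysis plan cannot use dates and advice that were not captured during follow-up, and capture is a matter for the protocol.

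**Conclusion.** The point holds as a plausible differential bias of unknown size. It rests on three features of the protocol: the listed outcomes include contacts that the route can prompt, the outcome period overlaps the symptom reporting, and the trigger is tied to what separates Long COVID from Control Group 2 and probably from Control Group 1. The likely direction is upward, provided that net extra contacts per alert are positive.

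A reader might go further and infer that the study does inflate its own outcome. The protocol does not support that. It gives no severity threshold, alert rate, contact rate or share of advice that is acted on, so the illustrative ratios of 1.005 to 1.24 show only what assumed rates would do. The safety route is not in question. The change is worth making because it is cheap and because full records of alerts and advice may not be obtainable afterwards.

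**What to change.** 1. In section 8.2, keep as research data, against the Global ID, the date of every automatic notification, nurse or physician contact, GP contact and referral, together with the advice given. The letter already required after verbal contact carries much of this.
2. In sections 5.0 and 8.1, report the comparison of health service use with all contacts, and again without GP and hospital contacts that fall within a prespecified window after a logged alert. Present the two as bounds: alerts coincide with genuine flares, so the exclusion also removes real care, and more of it in Long COVID.
3. Show alongside these the rates before registration from CPRD and HES, when no study prompt could act. Section 8.1 sets how far the records run forward and does not rule out earlier ones.

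The safety route stays as written. The cost is one log on Atom5, some nurse time to complete it, and one or two further tables.
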